7. RISKS AND DISCOMFORTS

The following are potential risks/discomforts that participants may experience in this study:

- 1) **Assessments and Questionnaires.** During the study assessments, participants may feel bored or tired completing some of the questionnaires or computer tasks. They also might experience some discomfort, embarrassment, or anxiety from discussing personal material and completing self-report questionnaires. Likewise, some participants may feel uncomfortable about having assessment sessions digitally recorded and reviewed by study staff (which is necessary for rater supervision as well as assessment of the reliability of ratings).
- 2) **EEG.** There are no known or foreseeable risks or side effects associated the EEG procedures. The EEG sensors (Brain Products GmbH, Gilching, Germany) have been approved by the U.S. Food and Drug Administration (FDA) for research purposes and will be operated within the standards reviewed and accepted by the FDA. Participants may experience some discomfort because we may have to gently scrape the skin in order to receive clear signals from the EEG electrodes.
- 3) **Computer tasks.** Some of the scenes that participants will view during the Emotional Interference Task (EIT) involve emotionally evocative images of violence, death, blood/gore, and sex (from the International Affective Picture System [IAPS] dataset) and may generate distress.
- 4) **Treatment.** The treatment offered in this study may make some individuals temporarily distressed during procedures that involve confronting the content of their repetitive negative thoughts and associated emotions of depression and anxiety (e.g., mindfulness of thoughts and emotions; imaginal rehearsal tasks); however, these procedures rarely make subjects significantly distressed, and participants will be able to manage the intensity of these exercises along with their therapist. Participants may also experience an increase in distress due to the natural waxing and waning of OCD, anxiety, and depression symptoms; however, participants will be carefully monitored, and measures will be taken to minimize potential risks during the project period (as discussed in "Protection Against Risks" below).
- 5) **Privacy and Confidentiality.** Breach of confidentiality represents a potential risk; however, the greatest care will be taken to prevent this from occurring (as discussed in "Protection Against Risks" below). In the informed consent process, we will also inform participants of the legal limits to privacy and confidentiality including: (1) if we believe participants are at serious risk of harming themselves or another person, (2) if we learn of ongoing abuse or neglect of a child, disabled, or elderly person, and (3) if we receive a subpoena or court order. We currently have an active Business Associate Agreement with a Statement of Work for iMotions Inc to be able to share coded data collected and analyzed using their software platform (i.e., the eye tracking data) for data support purposes.

In addition to the above practices, our study will be under compliance with the HIPAA (Health Insurance Portability and Accountability Act) rules governing the Partners

Healthcare system. All participants who enroll in this study will be given an electronic copy of the HIPAA privacy notice and will be asked to sign an acknowledgement of receipt and authorization form.

Protection Against Risks

The following procedures will be implemented to protect participants against risks:

- 1) **Informed Consent.** Informed consent will be obtained at the virtual screening visit using IRB-approved e-consent forms. After participants read the consent form, the PI ([name]) or doctoral-level delegate will paraphrase each segment of the consent form and answer any questions. Participants will be clearly informed of the voluntary and confidential nature of their participation, the potential risks and benefits of the study, and their right to terminate treatment at any time without penalty. There will be a clause included in the informed consent form concerning the audio taping of assessments and therapy sessions for reliability. As of February 2022, participants will be shown sample images from the IAPS database so they can decide whether to participate in the EIT task since the images may be distressing. Participants already enrolled prior to this change will not be re-consented because they have already seen the task and know what it entails. If the participant agrees to participate in the study, the consent form will be signed by the research participant and the PI using the e-consent module in REDCapTM. Each participant will be emailed a copy of the signed and dated consent forms.
- 2) **Assessments and Treatment.** The IEs will make every attempt to help participants feel comfortable when discussing sensitive material. Participants will have as much time as needed to complete study questionnaires and may skip any questions they do not want to answer. The therapist will work with the participant to ensure sessions are tolerable and appropriate in terms of risk and distress.
- 3) **EEG.** The experimenters will make every attempt to help participants feel comfortable during the EEG and will check in with participants regarding their comfort level during the set-up of the EEG sensors. Participants can ask to pause or stop the EEG session at any time, for any reason.
- 4) **Computer tasks.** Participants will be shown two sample images from the same database at the screening visit so they can decide whether to participate in the EIT. If they choose to participate in the task, they are also told that it is alright to look away during the task if they find these images too disturbing.
- 5) **Privacy and Confidentiality.** The following methods will be used to protect the confidentiality of information provided by participants:
 - a) Data will be encoded using Participant IDs and not names. IDs will be assigned sequentially and unrelated to name, social security number, or other easily identified information.
 - b) Names will not be included in digital recordings, in computerized data files, or in any published reports.
 - c) Digital recordings for reliability, adherence, and competence will be stored securely in a password-protected drive within the Center for OCD and Related Disorders and destroyed after completion of the study.
 - d) Study data will be reviewed only by pre-designated study personnel or, if necessary, by institutional, state or federal regulatory personnel.

- e) All personnel will be trained in research confidentiality procedures and will be educated about the importance of strictly protecting participants' rights to confidentiality.
 - f) Many procedures will be used to protect the security of data collected via REDCapTM, the platform for electronic data capture that will be used in this study. REDCapTM is deployed on a secured server. All network connections to the server are encrypted using high strength cyphers of at least 128 bits. The hardware is owned by MGH/Harvard Medical School (HMS) and administered by several computer professionals employed by the MGH/HMS.
 - g) MGH is accredited by the Association for the Accreditation of the Human Research Protection Programs Inc. (AAHRP), indicating that it is an institution that has regulations and policies in place to ensure protection of research participants and their confidentiality that exceed federal requirements for safeguarding participants.
 - h) Data shared with iMotions Inc for data support purposes will only include participants' coded alphanumeric study IDs and the key to the coded data (linking study ID and participants' identifiable information) will not be shared. Thus, iMotions will not have the ability to link the data to individual participants. Files will be shared via PHS Secure File Transfer.
 - i) Any data that is shared with other collaborators in the future would only be done so after executing a formal Data Use Agreement from Massachusetts General Hospital (MGH). As part of this process, the final dataset would be stripped of any identifiers that would permit linkages to individual research participants prior to release for sharing (i.e., coded). Additionally, given the sensitive nature of psychiatric symptoms and diagnosis and our relatively small sample size, we would make the data and associated documentation available to users only under a data-sharing agreement that provides for: (1) a well-described justification for the use of the data; (2) a commitment to using the data only for research purposes (under purview of an institutional IRB) and not to identify any individual participant; (3) a commitment to securing the data using appropriate computer technology; (4) a commitment to not transfer the data to other users; and (5) a commitment to destroying the data after analyses are completed. In compliance with NIH guidelines, data sharing would be done in a timely fashion (i.e., no later than the acceptance for publication of the main findings for the final dataset).
 - j) Due to the NIH-funding for this study, a Certificate of Confidentiality will automatically be obtained.
 - k) All necessary precautions will be taken to ensure participant privacy while conducting virtual study visits over ZoomTM. Healthcare Secure ZoomTM includes built in protections such as chat encryption, mandatory waiting rooms, and disablement of video recordings.
- 6) Emergencies and Suicidality.** Because patients with affective disorders can also experience suicidal thinking and behaviors, we will carefully implement safety precautions including:
- a) Patients who are actively suicidal at the screening visit (as assessed by the SCID-5-RV, SIGH-D, and/or score on the BDI-II suicide item #9 ≥ 2) will be excluded from the study.
 - b) Screening procedures will also exclude any individuals at potentially greater risk for psychiatric deterioration or an adverse outcome, or who are not clinically suitable for the study protocol. For example, as described in the

inclusion/exclusion criteria above, individuals will be excluded if they have active and clinically significant homicidality or any features requiring a higher level of care.

- c) As part of the informed consent process, participants will be asked if they are willing to provide contact information for two friends or family members and to give permission to have the research team call or write to these individuals in the case of an emergency (i.e., if we have concerns about their wellbeing).
 - d) Suicidality will be closely monitored with the BDI-II suicide item (#9) and clinician inquiry at each visit.
 - e) Patients at higher risk will be withdrawn from the study as described in the next section below.
 - f) [name] (or covering clinician in her absence) will be available 24/7 to participants in the event of a clinical emergency; this will be clearly communicated orally and in writing to study participants (i.e., the consent form describes how to reach the investigators in an emergency). Participants will be referred for a higher level of care as needed.
 - g) In the event that a study staff member witnesses behaviors such as abuse or neglect of children or the elderly while conducting a virtual study visit via Zoom™, they will report this to the PI who will consult with the Office of General Council and follow hospital policy for reporting such behaviors.
- 7) **Participant Withdrawal.** Subjects may be withdrawn from the study for *any* of the following reasons:
- a) A significantly deteriorating clinical course, such as emergence of active suicidal ideation or a need for hospitalization.
 - b) Score of ≥ 2 on the BDI-II suicide item (#9) and subsequent evaluation by the PI indicating it would be unsafe for the patient to remain in the study.
 - c) Score of 6 (much worse) or 7 (very much worse) on the CGI-I for 3 consecutive weeks and therapist and PI judgment that remaining in the study is not in the subject's best interest; a patient may be withdrawn sooner than this, if in the judgment of the therapist and PI, this is in the patient's best interest.
 - d) PIs' decision that withdrawal from the study is in the subject's best interest.
 - e) Subject's decision to withdraw.

Subjects who require medication changes or begin other types of therapy (e.g., family therapy) will be kept in the study even though such events violate study procedures. We will compare outcome data for compliant and non-compliant subjects.

The PI will discuss and agree upon the withdrawal of any subject with the therapist and [name]. The reason for withdrawal or dropout will be documented, and the subject will be referred for appropriate treatment. Except for subjects who withdraw consent to participate, all who are withdrawn or drop out of the study will be asked to complete all remaining assessments. We will educate subjects about the importance of completing all scheduled assessments and will provide payment as described above to encourage retention. As mentioned above, participants will be asked if they are willing to provide contact information for two friends or family members and to give permission to have the research team call or write to these individuals if contact between the participant and the research team is lost.

The above procedures have been used in previous research studies and were effective in protecting our research participants against risk. Therefore, we anticipate that these procedures

will be effective in our proposed study. In the unlikely event that a participant experiences a research-related injury, the study PI will arrange for appropriate treatment.

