Emotional Interference Task (EIT)⁷⁰: The EIT measures difficulties *sustaining attention* in the presence of distressing emotional contexts. Participants view 40 neutral and 40 arousing (20 pleasant and 20 unpleasant) photographs from the International Affective Picture System (IAPS)⁷¹ for 6 seconds each, in random order, with a 1-second interval between pictures (148 trials). A high- or low-pitched tone is played either 1 or 4 seconds after each picture is presented, and participants are instructed to choose whether each tone is high or low by pressing a button as quickly as possible after each tone is played. Mean reaction times are calculated separately for pleasant, unpleasant, and neutral pictures. Emotional interference is then calculated separately for pleasant and unpleasant stimuli by subtracting mean reaction times recorded while viewing neutral pictures from mean reaction times recorded while viewing pleasant and unpleasant pictures. Faster reaction times reflect better ability to inhibit emotional interference while sustaining attention on the tone; we will also collect gaze data to validate for future research. Past research has indicated that patients with GAD demonstrate slower reaction times on the EIT vs. controls, and symptom improvement is associated with faster reaction times.^{43,72} The EIT will be administered at the following timepoints: baseline (week 0), mid-treatment (week 4), and post-treatment (week 8). Computer task sessions will occur within a 7-10-day window, but no longer than 14 days, from each clinical assessment visit.

Psychophysiological Measurement. Galvanic Skin Response (GSR) will also be measured during the EIT at baseline, mid-treatment, and post-treatment. Biometric measurement of this psychophysiological index will be recorded using the iMotions platform.

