Randomization

At the baseline visit, eligible subjects will be randomized (1:1 in parallel) to AR-ERT or SPT using the REDCapTM database.

Treatment

For all participants, treatment will consist of 8 weekly sessions provided via Healthcare Secure ZoomTM that are 60 minutes in duration. Eight sessions is the length of ERT currently being tested,^{107,108} allowing us to directly compare our effect sizes with the full package. All sessions are individual treatment (no group treatment).

Attention Regulation – Emotion Regulation Therapy (AR-ERT)

A brief, manualized version of individual Emotion Regulation Therapy (ERT) focused on the Attention Regulation module will be administered to patients randomized to AR-ERT. Specifically, the 8-session protocol will be a streamlined version of ERT, which tested as part of a NIH-sponsored R34:MH070682. The full protocol^a engages several active mechanisms (i.e., attention regulation, metacognitive regulation, reward/threat processing) and an 8-session version of this full treatment is currently being studied; however, in order to test the target of attentional/cognitive control, we are focusing solely on attention regulation skills: (a) Orienting (i.e., the ability to flexibly shift attention) via mindfulness of the breath (sessions 1-4), and (b) Allowing (i.e., the ability to sustain attention despite unpleasant emotional experiences) via mindfulness of thoughts and emotions (sessions 5-8). Treatment will also include lessons for practicing these skills in two different contexts: (a) reactive: reviewing challenging (i.e., emotion-laden) situations that have happened in the past week in which attention regulation skills could have been applied to counter automatic reactive RNT responses (sessions 1-4) as well as (b) proactive: preparing for challenging situations that may happen in the future in which skills could be implemented (sessions 5-8).

Specifically, session 1 provides patients with a model of how RNT maintains emotions, presents between-session self-monitoring of RNT, and introduces the attention regulation skill of Orienting via mindfulness of the breath. In sessions 2-4, Orienting skills continue to be practiced. Patients review their self-monitoring forms to detect triggers and consequences of RNT. They also conduct in-session imaginal rehearsal of situations from the past week that

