Our multi-level generalized linear modeling (GLM) approach (described below under “Primary Analyses”) uses an intent-to-treat analysis that includes all participants, regardless of missing data (increasing power and generalizability), and it provides accurate estimates of regression coefficients in small samples.^{118,119} Despite our best efforts to retain participants, we do expect dropouts (i.e., subjects who are lost to follow-up or withdraw early from the study for reasons described below under “Participant Withdrawal”). We will attempt to perform all scheduled assessments for subjects who are withdrawn from the protocol and will provide financial incentives for participation in assessments.

Missing data rates and patterns will be assessed by treatment arm. Reason(s) for missing data will be documented, and we will evaluate reasons for dropout, study withdrawal, and loss-to-follow-up by treatment group. We will attempt to ascertain if missingness is occurring at random by evaluating factors associated with dropout for potential attrition bias. We will also compare study dropouts to study completers on demographic and clinical variables. Finally, we will use sensitivity analyses to quantify the impact of missing data.¹²⁰

Data Processing

For behavioral tasks that include reaction times (e.g., the Emotional Interference Task [EIT]), we will remove reaction times <150 ms given that such responses are rare and likely represent errors.¹²¹ Eye position fixations from the Attentional Engagement-Disengagement Task (AEDT) sampled at 120Hz will be converted to visual fixation data using standard criteria (i.e., minimum duration 100ms; minimum radius 1 degree).¹²²

Eye-blink artifacts will be removed from scalp-recorded EEG data on the Cued

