Emotional Control Task (CECT) and during the resting-state period (0.1-100Hz, sample rate = 256Hz) using established procedures,¹²³ and gross artifacts will be rejected by visual inspection. For the CECT, cue- and target-locked event related potentials (ERPs) will be formed by segmenting EEG data around cue and stimulus onsets (from -200 ms to 1000 ms post-stimulus) and averaging the segments. Start and end points for the components of interest are: (a) cue-locked N2: 200-350ms post-cue; (b) target-locked N2: 200-350ms post-target; (c) target-locked N450: 400-500ms post-target; (d) target-locked P300: 300-600ms post-target.⁴⁹ ERPs will be rejected if there is significant artifact (e.g., amplitude $\pm 100 \mu\text{V}$) at any electrode on a given trial. Artifact-free mean amplitudes (μV) will be extracted for ERP analyses. Additionally, nonoverlapping, artifact-free 2-second epochs from the resting-state period will be extracted for source localization analyses. Building on recent source localization studies,^{80,124} seeds from key regions within the frontoparietal (FPN) and default mode (DMN) networks will be selected to create regions of interest (ROIs) based on previous published methods^{125,126} and drawing from the Montreal Neurological Institute 305 template.¹²⁷ We will then compute EEG source-based functional connectivity using exact Low Resolution Electromagnetic Tomography (eLORETA) software.⁷⁸

Primary Analyses

Due to the nested structure of the data (i.e., 4 assessments per participant), we will use a multi-level generalized linear modeling (GLM) approach to address each of our hypotheses.

Hypothesis 1: Target Engagement. To test whether participants who receive AR-ERT show greater improvements in attentional/cognitive control relative to those who receive SPT, we will run a series of GLM analyses for each index of our attentional/cognitive control target:

- 1) **Behavioral:** (a) attentional disengagement (i.e., latency of shift in gaze from emotional to neutral face surrounded by the frame; AEDT), and (b) sustained attention (i.e., difference in reaction times to tones following a negative vs. neutral stimulus on the EIT),

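### Participants may look away from EIT pictures, but the sustained-attention index has no viewing check, so avoidance can score as reduced interference

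*Combined protocol and SAP*

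**What the plan says.** Section 5 (Emotional Interference Task) computes interference by "subtracting mean reaction times recorded while viewing neutral pictures from mean reaction times recorded while viewing pleasant and unpleasant pictures". It gives the direction of scoring as "Faster reaction times reflect better ability to inhibit emotional interference while sustaining attention on the tone". Of the gaze recorded during the task it says only that "we will also collect gaze data to validate for future research".

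Section 6 (Primary Analyses, Hypothesis 1) defines the sustained-attention index as the "difference in reaction times to tones following a negative vs. neutral stimulus on the EIT". For reaction-time tasks, Data Processing in the same section has one trial-level rule: "we will remove reaction times <150 ms given that such responses are rare and likely represent errors". The fixation criteria that follow are written for the other eye-tracking task, the AEDT.

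Section 7 (Protection Against Risks, Computer tasks) lets participants decline the EIT after seeing sample images. For those who take part, "they are also told that it is alright to look away during the task if they find these images too disturbing".

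**The concern.** The index is meant to show how far a distressing picture slows the response to a tone, and its definition takes for granted that the picture is being viewed. A participant who turns away from an unpleasant picture meets a weaker distractor. The tone response then moves toward the neutral-picture response, and the trial counts as good control. Resisting interference and removing its source give the same score.

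Looking away is unlikely to be random noise. The instruction ties it to finding a picture too disturbing, so it should concentrate on unpleasant pictures and on more distressed participants, and it may change as symptoms change.

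Two results are exposed. The first is the week 8 arm contrast for the EIT, an index under the primary aim. Section 6 analyses each index individually and without multiplicity adjustment in order to pick targets for later studies, so a distorted EIT result could by itself keep or drop a target. The second is Hypothesis 2b, which correlates pre-to-post EIT change with change in repetitive negative thinking, symptoms and functioning. If look-away moves with distress, part of any such correlation, or of its absence, would reflect viewing and not attentional control.

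**Working it through.** **The plan's own figures (Section 6, Power Analysis and Sample Size).** Inputs: 52 completers, 1:1 allocation (26 per arm), standardized effect 0.8, significance level .05 (two-sided). A two-group one-way ANOVA is equivalent to the two-sided t-test; the noncentral t distribution with 50 degrees of freedom and noncentrality 0.8 × √(26/2) = 2.88 gives power 0.807, matching the stated 80%. For the correlations, Fisher's z gives tanh[(1.960 + 0.842)/√(52 − 3)] = 0.380, matching the stated .38.

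**What look-away could do.** The documents give no look-away rate and no EIT mean or standard deviation (SD), so the following values are assumptions:

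- a looked-away unpleasant trial carries no interference, and neutral trials are unaffected;
- the true effect on viewed trials is 0.8 SD in favor of AR-ERT;
- m is the true mean interference in SPT, in SD units, varied from 0.8 to 2.0; the true AR-ERT mean is m − 0.8;
- a_S and a_A are the shares of unpleasant trials looked away from in SPT and AR-ERT;
- there are 26 participants per arm and the SD does not change.

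Observed effect: d = m(1 − a_S) − (m − 0.8)(1 − a_A).

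With a_S = 30% and a_A = 10%:

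- m = 0.8: 0.8 × 0.7 − 0 × 0.9 = 0.56
- m = 2.0: 2.0 × 0.7 − 1.2 × 0.9 = 1.40 − 1.08 = 0.32

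| SPT look-away | AR-ERT look-away | Observed d (m = 0.8 to 2.0) | Power |
|---|---|---|---|
| 0% | 0% | 0.80 | 0.81 |
| 10% | 10% | 0.72 | 0.72 |
| 20% | 20% | 0.64 | 0.62 |
| 20% | 10% | 0.64 to 0.52 | 0.62 to 0.45 |
| 30% | 10% | 0.56 to 0.32 | 0.51 to 0.20 |
| 10% | 30% | 0.72 to 0.96 | 0.72 to 0.92 |

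**With no true arm difference**, the spurious difference is m(a_A − a_S). At 30% in SPT and 10% in AR-ERT it is 0.8 × (−0.20) = −0.16 SD to 2.0 × (−0.20) = −0.40 SD, against AR-ERT. With the rates exchanged it is +0.16 to +0.40 SD, in favor of AR-ERT.

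**Direction.** Section 5 describes two AR-ERT skills. Allowing, in sessions 5-8, is "the ability to sustain attention despite unpleasant emotional experiences", which could reduce looking away. Orienting, in sessions 1-4, trains flexible shifting of attention, which could increase it. Nothing in the documents says which would prevail at week 8.

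**The case against.** The strongest objection concerns the construct. In this task the picture is the distractor and the tone is the target, and Section 1 counts shifting attention away from a stimulus as part of attentional control. Turning from picture to tone is then partly the skill being measured. This stands to a degree: avoidance and control are not cleanly opposite. But the score cannot tell them apart, and the task is described as measuring sustained attention in a distressing context, which looking away weakens.

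The illustration may also overstate the effect. Tones come 1 or 4 seconds after picture onset, so interference may already have begun, and looking away may itself slow the response. Since February 2022 participants have been shown sample images before choosing whether to do the EIT, which may remove some who would look away most. Both points stand, and they are reasons not to rely on the assumed rates.

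The consequence is limited. The EIT is one of seven Hypothesis 1 indices (two behavioral, four electrophysiological, one self-report) in a pilot trial, and the named primary outcome, the PTQ-PW, does not depend on it.

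A reader might infer that the index is biased specifically against AR-ERT, because Allowing should keep its patients looking at the pictures. The documents do not support that, since Orienting could work the other way. A reader might also infer that participants learn to avoid pictures they saw at earlier visits, but no section says the same pictures are reused. Nor does it follow that a gaze-filtered score should become the Hypothesis 1 index. A rule that accepts any fixation before the tone would pass most trials with a glance followed by avoidance. Any viewing filter also selects trials on behavior after randomization, so the arms could be compared on different sets of pictures.

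**Conclusion.** The point holds as an unhandled ambiguity in one Hypothesis 1 index. The permission to look away, the reaction-time-only score, the single 150 ms filter and the unused gaze data are all explicit in the documents. That avoidance can score as reduced interference is an inference from the scoring rule; it rests on an unviewed picture interfering less than a viewed one.

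Neither sign nor size can be fixed from the documents. Equal look-away in both arms dilutes the contrast, and unequal look-away can bias it either way. The figures above depend on assumed look-away rates, an assumed range for mean interference and zero interference on unviewed trials, so they show what is possible, not what to expect. As planned, an EIT result for or against AR-ERT cannot be attributed to attentional control without knowing how much viewing differed. The remedy is cheap and worth making.

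**What to change.** Keep the permission to look away, and keep the all-trials reaction-time index for Hypothesis 1. Then, before arm-level EIT data are examined:

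1. In Section 6, Data Processing, define a per-trial gaze measure for the EIT, for example the proportion of time from picture onset to tone spent on the picture, and whether gaze is on the picture at tone onset. State the threshold for a viewed trial, and separate loss of tracker signal from gaze that is off the picture.
2. Report the measure by picture type, arm and visit.
3. Prespecify a sensitivity analysis of the EIT results for Hypotheses 1 and 2b restricted to viewed trials.
4. State that an EIT arm difference will be read as target engagement only if differential look-away does not explain it.

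The cost is SAP wording and extra processing of gaze data already recorded. The sensitivity analysis will have fewer trials. How many fewer is hard to judge, because Section 5 lists 40 + 40 = 80 pictures, shown "for 6 seconds each, in random order, with a 1-second interval between pictures (148 trials"), and the two counts should be reconciled. That analysis also conditions on viewing after randomization, so it supports the all-trials index and does not replace it.
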